### **13.2. Analysis of Efficacy and Sample Size**

Using data collected at each of Study Visits 2, 3, and 4, percent change from screening at each time point will be calculated for each patient with respect to frequency of OAB symptoms, including 3-day daily averages of daytime voids, urge events, nighttime voids, and urge incontinent events. The maximum percent improvement across the four symptoms will also be calculated at each time point as a composite endpoint. Percent improvement in daily average total voids relative to an upper normal limit of 8, will also be calculated, and will be bounded below at 0% for patients not achieving improvement and bounded above at 100% for patients achieving or surpassing the upper normal limit of 8. Longitudinal analyses will be performed using repeated measures models to assess and describe trends over time with respect to these endpoints. At individual time points, the one-sample T-test will be performed at significance level  $\alpha=0.05$  within each treatment group and for the pooled study groups to assess the mean percent improvements, with 95% confidence intervals for mean percent improvements also calculated. The percent change endpoints are not likely to have approximately normal distributions, but the sample size is considered sufficient such that mean values will be approximately normally distributed, justifying the use of the T-tests. If there is concern with the distributions, then the Wilcoxon signed rank test will be used as an alternative to the one-sample T-test.

Sample size is evaluated by the performance of the 95% confidence interval for mean percent improvement percent improvement in daily average total voids relative to an upper normal limit of 8. Log ratios of daily average event frequencies at post-screening time points relative to the daily average event frequencies at baseline, which are mathematically related to the percent changes from baseline, are more likely than percent changes to have approximately normal distributions. If such log ratios are normally distributed so that in both treatment groups the median percent improvement (toward zero) in daily average total voids is 15% and so that 25% of patients will achieve a 50% improvement, then with a total evaluable sample size of 80 patients completing the study, there is an estimated 95.6% power to conclude that the mean percent improvement in daily average total voids relative to an upper normal limit of 8 is 25% or larger using the 95% confidence interval. Within each treatment group of size  $n=40$ , there is an estimated 90.8% power to conclude that the mean percent improvement in daily average total voids relative to an upper normal limit of 8 is 20% or larger using the 95% confidence interval.

Two-sample T-tests performed at a significance level  $\alpha=0.05$  will be used to compare the treatment groups with respect to mean percent improvements in frequency of OAB symptoms, and with respect to results of OAB questionnaires. If there is concern with the non-normality of the distributions of these endpoints, then the Wilcoxon rank sum test will be used as an alternative to the two-sample T-test. Linear models will be constructed as extensions of the one-sample and two-sample T-tests to allow for assessments of mean percent improvements and group comparisons with covariate adjustments.

Frequencies of responders at individual time points and over all time points will also be calculated, where a responder for a given OAB symptom is defined as a subject achieving 50% improvement in frequency, and a responder for the composite collection of OAB symptoms is defined as a subject achieving 50% improvement in frequency for at least one symptom frequency. The treatment groups will be

compared with respect to response frequencies using chi-square or Fisher's exact tests, and exact 95% binomial confidence intervals will be calculated.

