Study design	
Subjects that have signed the Informed Consent Form and meet all applicable eligibility criteria will be randomized 1:1 to 30-minute stimulation treatments either once a week or three times a week over a treatment period of 12 weeks.
 
Subjects will return to the clinic at 1-, 4-, 8-, and 12-weeks post-baseline for visit assessments listed in the Schedule of Activities. Investigative sites may elect to have some visits completed remotely via use of ePRO for visit questionnaires. On weeks where a subject does not have an in-clinic visit, they will be contacted by phone and queried for health and medication changes and any device issues. At the end of the first 12 weeks of stimulation, subjects will return to the clinic for final assessments, then will either enroll in the long-term follow up phase, if eligible, or exit from the study.

Statistical Methods	
Analyses will be performed within both the intent-to-treat (ITT) population of all enrolled patients and among the subset of patients who complete the study. Patients may be missing endpoint data at one or more, or possibly all, post-screening time points, at which endpoint data will be provided by carrying forward the most recent observation. Enrollment will continue until 80 patients complete the study. Expecting 15% dropout, the anticipated total enrollment will be approximately 94 patients.

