#### **7.10. Visit 4 - Week 8 ± 4 days**

This visit will be scheduled after 8 weeks of therapy for evaluations. This visit may be performed remotely via ePRO.

Step	Action
1.	Subjects will be queried for AE/SAE or concomitant medication changes.
2.	The 3-day Bladder Diary dispensed at Visit 3 will be collected and reviewed.
3.	Applicable visit forms and questionnaires will be completed
4.	Subjects will be given a new 3-day Bladder Diary to complete in the days leading up to the next scheduled study visit.

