#### **7.11. Visit 5 – Week 12 ± 4 days**

This visit will be scheduled after 12 weeks of stimulation for final evaluations.

Step	Action
1.	Subjects will be queried for AE/SAE or changes to concomitant medications.
2.	The 3-day Bladder Diary dispensed at Visit 4 will be collected and reviewed.
3.	Applicable visit forms and questionnaires will be completed, including the Study Exit Form.
4.	The subject will be asked questions regarding the feeling of the therapy and ease of use of the Test Article.
5.	Subjects will either exit from the study or be given the option to enroll in the long-term follow-up study, if eligible.

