## **17.2. Justification of study design**

Electrical stimulation of peripheral nerves has been used to manage chronic pain, Parkinson's disease, epilepsy, and other neurological disorders. These treatments include placing electrodes over the spinal cord, in deep brain structures, and over nerves in the periphery, etc. Recently, PTNS has been used to treat subject with OAB. PTNS is thought to modify the signals from the bladder to achieve its effect, it usually takes 5-7 weeks for symptoms to change. However, patients respond at different rates. In a review of about 100 patients who responded to PTNS, onset of symptom relief began anywhere between 2-12 weeks after starting treatment. For about 20% of these patients, some symptoms didn't improve until after 8 weeks [1]. However, PTNS therapy is performed only in a doctor's office during weekly visits and requires that a needle-electrode is blindly inserted through the patient's skin near their inner ankle. A non-invasive transcutaneous system that can be used at home will make treatment more accessible and convenient for patients, will help to improve treatment compliance and subject satisfaction and may contribute to better outcomes.

Once subjects meet all eligibility and screening criteria, they will be enrolled in the study. Subjects will be randomized to therapy once a week or three times a week for 12 weeks. Unlike PTNS, the Test Article is fully non-invasive and can be done completely at home, eliminating the need for weekly visits to a medical office. This study is designed to minimize patient and site contact to help reduce possible exposure to COVID 19. The only required in-person office visit would be to conduct EMG screening to confirm eligibility for enrollment and to set up the System for home use, and end of study assessments. To further minimize COVID19 exposure, this protocol enables sites to combine Screening Visit 2 and Visit 1/Baseline in a single office visit.

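### Section 13.2 builds the diary efficacy endpoints from Visits 2, 3 and 4 (Weeks 1, 4 and 8) and leaves out the end-of-treatment diary collected at Visit 5 (Week 12)

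*Combined protocol and SAP*

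**What the plan says.** The efficacy plan in Section 13.2 opens with the visits that supply the diary data: "Using data collected at each of Study Visits 2, 3, and 4, percent change from screening at each time point will be calculated". The symptoms are daytime voids, urge events, nighttime voids and urge incontinence events. The same section then adds the composite (largest improvement across the four symptoms), the improvement in total voids toward the limit of 8, repeated measures models, one-sample tests and two-sample tests. It also plans responder rates: "Frequencies of responders at individual time points and over all time points will also be calculated". None of these sentences names a further visit. The two-sample comparisons extend to the questionnaires ("and with respect to results of OAB questionnaires"), again without naming a visit.

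The visit sections fix the calendar. For Visit 4, Section 7.10 says: "This visit will be scheduled after 8 weeks of therapy for evaluations". For Visit 5, Section 7.11 says: "This visit will be scheduled after 12 weeks of stimulation for final evaluations". At Visit 5 a diary comes in: "The 3-day Bladder Diary dispensed at Visit 4 will be collected and reviewed". The study design row of the Protocol Summary (Section 2) gives that visit the same role: "At the end of the first 12 weeks of stimulation, subjects will return to the clinic for final assessments".

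**The concern.** The first objective in Section 4 is to compare the two session frequencies, and the treatment period is 12 weeks. The natural time for that comparison is the end of treatment, when the two groups differ most in the number of sessions received. The written rule stops at Week 8.

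If the rule is followed, the symptom endpoints have no planned end-of-treatment result, either within a group or between groups. If it is not followed, a Week 12 diary result falls outside the written plan. That is awkward here because the study is unblinded (Section 6.1) and its data are meant to support a 510(k) clearance (Section 17.1). A time point chosen once open-label data are in view is easy to challenge.

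As context only, Section 17.2 says of percutaneous stimulation that "it usually takes 5-7 weeks for symptoms to change", and that in about 20% of responders some symptoms improved only after 8 weeks. Those statements concern a different device, and no loss of response for this trial can be derived from them.

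**Working it through.** **Visit map** (Sections 7.2 and 7.8 to 7.11, set against the list in 13.2):

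| Visit | Week | Window | Diary collected | Named in 13.2 |
|---|---|---|---|---|
| 2 | 1 | ±2 days | yes | yes |
| 3 | 4 | ±4 days | yes | yes |
| 4 | 8 | ±4 days | yes | yes |
| 5 | 12 | ±4 days | yes | no |

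The schedule table under Section 7.12 was not readable in the text available. Sections 7.2 and 7.11 are enough to establish Visit 5 as Week 12 with a diary.

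**Does anything else in Section 13 bring Week 12 in?** Section 13.1 speaks of time points after screening, and 13.2 of individual time points and all time points. These phrases refer back to the visits already listed and do not add one. No sentence in Section 13 names Visit 5 or Week 12.

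**Time left uncovered.** Visit 4 falls on day 56 ± 4 (52 to 60) and Visit 5 on day 84 ± 4 (80 to 88).
- Nominal gap: 84 − 56 = 28 days.
- Shortest gap: 80 − 60 = 20 days. Longest gap: 88 − 52 = 36 days.

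**Planned sessions after Week 8.**
- Once weekly: 12 − 8 = 4 of 12 (33%).
- Three times weekly: 36 − 24 = 12 of 36 (33%).
- Between-group difference in cumulative sessions: 24 − 8 = 16 at Week 8, and 36 − 12 = 24 at Week 12.

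**Diaries.** If each of 80 completers returns all four post-baseline diaries, there are 80 × 4 = 320. The Visit 5 diaries are 80 of these (25%), or 80 × 3 = 240 diary-days.

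**Do the plan's own sample-size figures depend on the visit list?**
- Enrolment: 80 / (1 − 0.15) = 94.1, which agrees with the stated 94.
- Power: Section 13.2 assumes normal log ratios with median improvement 15% and 25% of patients reaching 50% improvement. This gives SD = (ln 0.85 − ln 0.5) / z(0.75) = 0.787. The baseline void count is not stated, so it was varied as a fixed value from 10 to 20 per day in a simulation of 20,000 trials per setting. Improvement was (baseline − follow-up) / (baseline − 8), held between 0 and 100%. Success meant that the lower limit of the two-sided 95% t interval exceeded the threshold.

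| Assumed baseline voids per day | n=80, threshold 25% | n=40, threshold 20% |
|---|---|---|
| 10 | 99.95% | 99.0% |
| 16 | 96.2% | 91.8% |
| 17 | 94.8% | 90.5% |
| 20 | 88.0% | 84.0% |

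The stated 95.6% and 90.8% are attainable at an assumed baseline of about 16 to 17, but they cannot be confirmed from the documents alone. The calculation is not tied to any visit, so adding Visit 5 changes neither the power nor the enrolment figure.

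**The case against.** The best case for the plan has four parts.

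First, only one sentence carries the list. The two-sample tests and responder analyses name no visit, the general wording about time points could be read to include Week 12, and nothing forbids analysing it. A careful analyst would probably ask. That is fair, but general wording does not extend an explicit list, and a plan should not depend on someone querying its end-of-treatment time point.

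Second, the list may be a slip. A similar diary-number mismatch appears in the long-term phase: Section 8.9 has Visit 11 collecting the Visit 8 diary, while Section 8.11 dispenses one at Visit 10. That is weak evidence, because Section 8 was added in Version 2 and the amendment summary lists no specific change to Section 13. If the numbers were shifted, Visits 3, 4 and 5 might have been meant. The documents do not settle this. Adding Visit 5 while keeping the already listed Visit 2 is sound on either reading.

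Third, completion of the study is not defined. Visit 5 is the likelier meaning for the 80 completers, since subjects not entering follow-up exit there, but Section 8.9 labels Visit 11 the end of study. The remark that completers may be defined by a visit whose diary is not analysed is therefore an inference, and the finding does not need it.

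Fourth, the diary and session counts only restate that one visit of four is missing. They do not measure an effect on results. That stands.

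**Conclusion.** The concern holds, and the text must be corrected before analysis. Section 13.2 as written takes the diary endpoints from Weeks 1, 4 and 8 and omits Week 12, the end of the treatment period under comparison. The omission is one of four post-baseline diary time points. It leaves nominally 28 days (20 to 36 within the visit windows) and one third of planned sessions after the last analysed diary, and it drops the point where the planned exposure difference is largest (24 sessions rather than 16).

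The diary count assumes complete returns from 80 completers, and the session counts assume full adherence. No bias, loss of response or loss of power can be calculated from the documents. The conclusion is limited to the diary endpoints; the questionnaire comparisons are not expressly affected.

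**What to change.** In Section 13.2, replace the visit list with Study Visits 2, 3, 4 and 5 (Weeks 1, 4, 8 and 12). Giving the weeks beside the visit numbers guards against another numbering error. That edit is sufficient for this point.

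A separate, secondary suggestion is to name Visit 5 / Week 12 as the main time point for the between-group comparison and for the confidence-interval criterion in the sample size paragraph, with the earlier visits supportive.

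The cost is wording only. The Week 12 diary is already dispensed at Visit 4 and collected at Visit 5. No visit, subject or data item is added, and the sample size is unchanged. The change should be made and dated before the Week 12 diary data are examined by group.

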### 3. Introduction

Overactive bladder is a stressful and disruptive chronic disorder that affects more than 16% of the adult population [1], an estimated 42 million adults in the just the United States alone. The symptoms of OAB cause millions of individuals to suffer with a decrease in their quality of life and put them at increased risk of falls, bone fractures due to falls and higher rates of anxiety and depression

OAB is characterized by four symptoms; urgency, frequency, nocturia, and urge incontinence[2]. Urgency is the complaint of a sudden, irresistible desire to pass urine which often is difficult to resist. Frequency is the number of voids per day. In OAB, there are usually 8 or more voiding episodes during waking hours. Nocturia is the number of voids per night. In OAB, the complaint of sleep interruption due to the need to void is 1+ times, per night. Urge incontinence is the involuntary leakage of urine, associated with sudden compelling desire to void. In order to be diagnosed, these symptoms or a combination of them, must be present without a pathologic or metabolic component causing them[3].

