## 7.6. Visit 1- Baseline Evaluations

These evaluation procedures outline the baseline evaluation that will take place before a subject begins stimulation therapy. These procedures can also be done during the Screening 2 / Baseline visit.

Step	Action
1.	The inclusion and exclusion criteria will be confirmed as being met
2.	Demographic information will be collected.
3.	OAB questionnaires will be completed including: 1. OAB-q 2. IIQ-7 (only for those with incontinence) 3. I-QoL 4. and OHQ
4.	Subjects will be randomized 1:1 to perform 30-minute stimulation sessions once per week or three times per week for the 12-week treatment period.

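### Testing the best-of-four symptom composite against zero in a single group can show improvement from diary noise alone; its single-group result should be descriptive only

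*Combined protocol and SAP*

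**What the plan says.** Section 13.2 (Analysis of Efficacy and Sample Size) computes percent change from screening for four diary symptoms: daytime voids, urge events, nighttime voids and urge incontinent events. It adds a composite: "The maximum percent improvement across the four symptoms will also be calculated at each time point as a composite endpoint". The same paragraph plans a one-sample T-test at 0.05, with 95% confidence intervals, "within each treatment group and for the pooled study groups to assess the mean percent improvements". If the distributions give concern, "the Wilcoxon signed rank test will be used as an alternative to the one-sample T-test". The composite is not exempted from these tests, and no null value is written down.

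A composite responder is "defined as a subject achieving 50% improvement in frequency for at least one symptom frequency". Responder frequencies get exact binomial intervals and a between-group test; no single-group responder test is planned.

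The numerical thresholds in 13.2 belong to another endpoint, percent improvement in total voids towards 8, bounded between 0% and 100%. Sample size is judged by whether that mean "relative to an upper normal limit of 8 is 25% or larger using the 95% confidence interval" in the pooled group, or 20% or larger per arm. Two-sample T-tests compare the arms.

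**The concern.** A maximum over four noisy changes has a higher expectation than any one of them. If nothing changes, each patient still has some symptom that happened to be lower at follow-up, and the composite picks it. A test of the composite mean against 0% is then not a test of benefit, and a larger sample makes false rejection more likely wherever that mean is above zero.

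This matters because evaluating overall effectiveness is a stated objective (Section 4), both arms receive stimulation without blinding (Section 6.1), no primary endpoint is named, and Section 17.1 says the data will support 510(k) clearance. With no untreated group, overall effectiveness can be judged only from single-group results. A significant composite p-value could be presented as effectiveness when noise alone can produce it.

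**Working it through.** **Inputs from the plan.** 80 completers, 40 per arm; four symptoms from 3-day diaries; two-sided 0.05, so 2.5% nominal in the direction of improvement. For total voids the power model assumes that "in both treatment groups the median percent improvement (toward zero) in daily average total voids is 15" percent and that 25% of patients improve by 50%. The implied SD of the log ratio is (ln 0.85 − ln 0.50)/z(0.75) = (−0.1625 + 0.6931)/0.6745 = 0.787. This is a spread of treated response, so it is taken as an upper-end value for noise.

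**The plan's own figures.** None is given for the composite. The stated powers for total voids are 95.6% (n=80, threshold 25%) and 90.8% (n=40, threshold 20%). Simulating log ratios from N(ln 0.85, 0.787), with improvement (B − P)/(B − 8) bounded to 0-1 (B baseline voids, P follow-up voids), gives 96.3% / 91.7% at B=16, 95.3% / 91.1% at 16.5 and 94.5% / 90.0% at 17. The figures therefore reproduce if baseline is near 16-17 per day. Baseline is not given and is an assumption; B=12 gives 99.7% / 97.6% and B=20 gives 88.0% / 84.3%.

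**Direction of the bias.** For four independent symmetric changes centred on zero, the maximum is positive with probability 1 − 0.5⁴ = 93.75%, and its mean is about 1.03 SD of one change. With common correlation ρ the shift on the log scale is 1.03 × SD × √(1 − ρ). At SD 0.2 and ρ 0.7 it is 1.03 × 0.2 × √0.3 = 0.113. Against it works log-normal skewness: an unchanged symptom with median ratio 1 averages 1 − exp(SD²/2), which is −2% at SD 0.2 and −36% at SD 0.787.

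**Size, assumed range.** Noise SD, correlation and symptom rates are not in the documents. Each patient's value is max(1 − exp(x)) over equicorrelated normal log ratios x with no true change. The table gives the share of simulated trials in which the one-sample T-test against 0% favours improvement.

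| Model | Log SD | Correlation | Mean composite | n=40 / n=80 |
|---|---|---|---|---|
| A: median ratio 1 | 0.2 | 0.7 | +9% | 90% / 99.5% |
| A | 0.3 | 0.5 | +17% | 99% / 100% |
| A | 0.787 | 0.5 | +29% | 86% / 98% |
| A | 0.787 | 0.8 | +8% | 20% / 23% |
| A | 0.787 | 0.9 | below 0 | about 5% / 3% |
| A | 0.787 | 0.95 | below 0 | about 1% / below 0.5% |
| A | 0.5 | 0.95 | just below 0 | 4.5% / 3.4% |
| B: mean change 0% in every symptom | 0.2 to 0.787 | 0.8 | +9% to +33% | 87-88% / 98-99% |
| B | 0.2 to 0.787 | 0.95 | +5% to +17% | 33-42% / 55-57% |

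Model B sets the log mean to −SD²/2, which removes the skewness. There one symptom tested alone rejects in 3-8% / 3-6% of trials, so nearly all the excess comes from taking the maximum. In model A the composite mean falls to zero at correlation 0.99 for SD 0.2 and at 0.87 for SD 0.787.

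**Overlap between symptoms.** Section 3 defines one symptom partly through another: "Urge incontinence is the involuntary leakage of urine, associated with sudden compelling desire to void". A count model can build this in, with urge events a subset of day voids and incontinence a subset of urge events. At assumed rates of 9/5/2/2 per day (day voids, urge, night voids, incontinence) and no true change, the mean is +31% and rejection 100% / 100%. Without incontinence (three symptoms) it is +23% and 99.7% / 100%.

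**Fallback test.** The signed rank test addresses distribution shape, not selection: 92% / 99.8% at SD 0.2, correlation 0.7, and 48% / 76% at SD 0.787, correlation 0.8 (model A).

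**Between arms.** Both arms carry the same shift. The two-sample T-test on the composite, 40 v 40, rejects in 4.4-5.5% of null trials in all these settings.

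**Responder rate.** The noise-only any-of-four rate is 0.1% to 57% over the model A range and 4% to 30% in the count models, too wide to size.

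**Total voids under the same null.** With median ratio 1, the share of trials whose interval clears 20% (n=40) / 25% (n=80) is about 52% / 46% at SD 0.3 and baseline 10.5; 22% / 9% at SD 0.3 and baseline 12; 0.8% / 0% at SD 0.3 and baseline 16.5; and 58% / 54% at SD 0.787 and baseline 16.5.

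**The case against.** The strongest reply is that the tested hypothesis is inferred. Section 13.2 does not name the composite in its T-test sentence or write a null of 0%. That stands, and the first correction is to state both. It does not remove the concern: no exemption is given, and a composite interval lying above 0% would be read as improvement.

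Second, the size rests on assumed noise. This also stands. At large SD and very high correlation, skewness offsets the selection and the test is near or below nominal. That combination needs four symptoms to move almost as one, although nighttime voids are counted apart from daytime voids and Section 7.6 anticipates patients without incontinence. With skewness removed, inflation remains at correlation 0.95.

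Third, the composite is an added endpoint, its components are reported, the arm comparison is the first-listed objective, and Section 5.1 says the study helps plan a larger one. This limits the damage but does not make the single-group p-value valid.

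Fourth, a reader might infer that total voids with its non-zero thresholds is a safe substitute. It is not: the floor at 0% gives it a positive mean under noise, and over part of the assumed range it clears those thresholds with no true change.

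**Conclusion.** The concern holds for single-group results. On the natural reading of 13.2, a one-sample test of the maximum-of-four composite can declare improvement with no true change. Across most of the assumed range this happens many times more often than the nominal 2.5%; in the large-SD, high-correlation corner of model A it does not. The upward push from taking a maximum follows from the definition. Its net size depends on diary variance, correlation and skewness, none of which the documents give.

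A reader might go further and infer that the randomised comparison or the sample size is compromised. The documents do not support that: the arms share the bias, and sizing uses total voids. Nor is there an invalid responder test, since none is planned within a group; only a caution on interpretation applies there. The point should be fixed, but it is not fatal to the study.

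**What to change.** In Section 13.2:

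1. State which endpoints the one-sample tests cover and the null value of each. Exclude the maximum-of-four composite from single-group testing, and report its single-group mean and interval as descriptive, not as evidence of effectiveness.
2. Use the composite for inference only in the randomised between-arm comparison, labelled exploratory.
3. Add that the single-group any-of-four responder rate carries the same upward selection and is descriptive.
4. Base single-group tests on the four individually named symptoms, described as uncontrolled before-after changes. Say that they are subject to regression to the mean, at least for void frequency, because inclusion criterion 6 requires an average of 10 or more frequency events per day in the diary.
5. Attach to any single-group reading of total voids the caveat that its floor at 0% gives it a positive mean under noise alone.

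The cost is a few sentences, with no added patients, visits or data and no change to the sizing. A favourable-looking single-group composite p-value is given up.

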#### **4. Objectives**

- To compare the effectiveness of 1 treatment session per week to 3 treatment sessions per week on OAB symptoms using the Test Article.
- To evaluate the overall effectiveness
- To evaluate any side effects of the Test Article.
- To evaluate the tolerability, usability, and satisfaction of the Test Article.
- To evaluate the compliance by subjects using the Test Article.

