The current study involves testing a surgery-free and non-invasive wearable bladder modulation system in the home by subjects with OAB. In addition, the System, through sensors incorporated into the modulation garment, provide objective confirmation of tibial nerve activation at the beginning and through the modulation therapy which provides personalized treatment for each patient. The Test Article provides several benefits over PTNS. First, it is wearable eliminating any risks associated with a needle puncture. Second, it allows the patient to perform their therapy in their home, eliminating the need for weekly and monthly travel to a physician's office. Third, it will provide objective confirmation that the active tibial nerve stimulation is automatically adjusting the personalized stimulation level for each subject. The study will involve stimulating for 30 minutes transcutaneously over the tibial nerve, either 1 day or 3 days per week for a total of 12 weeks. The main risks to subjects participating in this study is the potential for skin irritation at the electrode site. We anticipate that the risk of pain in this study to be minimal. In the event of pain, the subject can stop the stimulation or continue at a reduced level. As a result of participating in this study, subjects may experience a temporary reduction in their OAB symptoms. Data collected from this study will help in the development of a new therapy to treat their OAB which may benefit them in the future

This study will compare two treatment frequencies, one session a week or three sessions a week for a 12-week treatment period, followed by an optional additional 21-month long-term follow-up phase. Pre-validation and pre-verification testing were done to ensure system functionality and safety for this study. There were no cadaver or animal model testing done with the Test Article. Voltage tests were done to ensure that the Stimulator would stay within the set voltage parameters. Testing was done to ensure the Test Article could run properly for the full 30-minute treatment duration.

Biocompatible materials were chosen for this system to reduce any allergic reactions.

The risks to subjects participating in this study are minimal. Although subjects may see some temporary improvement, there is minimal benefit in participating in this study. The data collected in this study will be used to support the 510K clearance of the Test Article.

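### Total-voids improvement is floored at 0% and given one-sample tests with no stated null; tested against 0 it rejects even when nothing has changed, so it cannot show effectiveness

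*Combined protocol and SAP*

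**What the plan says.** Section 13.2 starts from symptom frequencies, for which "percent change from screening at each time point will be calculated for each patient". It adds a second kind of endpoint: improvement in daily total voids measured as progress toward 8 a day. That endpoint "will be bounded below at 0% for patients not achieving improvement and bounded above at 100" percent, so a patient who stays the same or gets worse scores 0.

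At each time point a one-sample T-test at alpha 0.05 is planned "within each treatment group and for the pooled study groups to assess the mean percent improvements". If the distributions cause concern, "the Wilcoxon signed rank test will be used as an alternative to the one-sample T-test". No null value is given for either test, and one sentence covers the floored and unfloored endpoints alike.

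The sample-size text in the same section is built on the floored endpoint: with 80 completers, "there is an estimated 95.6% power to conclude that the mean percent improvement in daily average total voids" toward 8 is at least 25%, judged by the 95% confidence interval. For 40 per arm the figure is 90.8% against 20%. These two thresholds appear only there. The same text says that log ratios of follow-up to baseline frequency "are more likely than percent changes to have approximately normal distributions".

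**The concern.** A variable that is never negative has a mean above 0 as soon as some patients improve by chance. If diaries vary and nothing changes, about half the patients record fewer voids at follow-up and score above 0. The other half record more and score exactly 0. The floored mean is then truly above 0, and a test that finds this is correct but uninformative. The signed rank test has the same fault: zeros drop out and every remaining value is positive.

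The stakes come from how the result could be used. Section 4 lists as an objective "To evaluate the overall effectiveness", separately from the comparison of session frequencies. Section 6.1 has both arms using the device without blinding, so the one-sample result is the route to that objective. Section 17.1 adds: "The data collected in this study will be used to support the 510K clearance of the Test Article". A significant within-arm or pooled result against 0 could be reported as effectiveness when nothing had improved.

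**Working it through.** **Inputs from Section 13.2.** Median improvement 15%; 25% of patients reach 50% improvement; log ratios normal; n=80 pooled and 40 per arm; thresholds 25% and 20%; alpha 0.05. Sidedness is not stated, so two-sided is used to match the 95% interval.

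**Input the documents do not give.** The baseline distribution. Section 6 requires only an average of at least 10 frequency events a day. Assumed values: 12, 16.5 and 20 voids a day, and a uniform mix from 10 to 25.

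**Model.** B is baseline, R the follow-up/baseline ratio, ln R normal with mean ln(median ratio) and SD σ. The endpoint is Y = (B − B·R)/(B − 8), set to 0 if negative and to 1 if above 1. A test rejects when the lower 95% t-limit for the mean of Y exceeds the null. T-test cells use 20,000 simulated trials.

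**Step 1: reproduce the plan's power.** σ = (ln 0.85 − ln 0.50)/0.6745 = (−0.1625 + 0.6931)/0.6745 = 0.787. With median ratio 0.85 and B=16.5, power is 95.5% (n=80 against 25%) and 91.1% (n=40 against 20%). The 10–25 mix gives 95.5% and 91.2%. The plan states 95.6% and 90.8%, so the model matches.

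**Step 2: no median change, null of 0.** The T-test rejects in 100% of trials at n=40 and n=80, for σ from 0.1 to 0.787, at every assumed baseline. Signed rank (500 trials per cell; B=16.5; σ 0.1, 0.3, 0.787) also rejects in 100%. The unfloored log ratio rejects in 4.7–5.3% of the same no-change cells.

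**Step 3: voids 10% worse at the median (σ=0.1, B=16.5).** The share improving at all is Φ(−ln 1.1/0.1) = Φ(−0.953) = 17%. The T-test still rejects 0 in 64% (n=40) and 99% (n=80), and signed rank in 70% and 99.6%. The log ratio shows benefit in 0%.

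**Step 4: limit of the worsening result.** At 20% worsening (B=16.5), rejection is 100% at σ=0.787; 99% (n=80) and 71% (n=40) at σ=0.2; but only 6% and 0.4% at σ=0.1.

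**Step 5: the 25% and 20% thresholds with no median change (B=16.5).**

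| σ | Mean of Y | Exceeds 25%, n=80 | Exceeds 20%, n=40 |
|---|---|---|---|
| 0.3 | 19% | 0% | 1% |
| 0.4 | 24% | 1% | 8% |
| 0.5 | 28% | 8% | 23% |
| 0.787 | 35% | 54% | 58% |

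The last row is an upper case, in which all the on-treatment spread is unrelated to treatment. At B=12 and σ=0.3 the two rates are 8% and 22%.

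**Step 6: between-arm comparison.** The two-sample T-test on the floored endpoint (40 per arm, B=16.5, no difference) rejects in 4.8–5.2%, so its error rate is intact.

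**The case against.** The plan never says the null is 0. The only thresholds it attaches to this endpoint are 25% and 20%. Against those, at baseline 16.5, a no-change trial is almost never called a success when the SD is 0.3 or less. The first-listed objective compares session frequencies, and that comparison is sound. Unfloored symptom changes and responder rates would be reported alongside. The replacement test is also less powerful than the stated figures suggest.

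Much of this stands as a limit. The fault belongs to the test against 0, not to every use of the endpoint. The thresholds may or may not screen out noise, depending on a baseline distribution and an SD that the documents do not give. That part is therefore a request for inputs, not a finding of error.

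It does not remove the concern. The thresholds are used only to evaluate sample size and are not assigned to the one-sample tests. Those tests also cover the unfloored percent changes, for which 0 is the obvious null, so 0 is how an analyst would read the sentence. The unfloored results reduce the risk of misreading without removing it.

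**Conclusion.** The concern holds, and the plan is wrong as written. A one-sample test of the floored total-voids endpoint against 0 rejects in essentially every trial with no median change. This follows from the floor itself and held at every baseline and SD tried. Rejection under modest worsening is common but depends on spread: near certain for 10% worsening at most SDs, and rare for 20% worsening when the SD is 0.1.

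The comparison of one with three sessions a week is not invalidated, and the four unfloored symptom changes are outside the point. Whether 25% and 20% are safe criteria cannot be settled from the documents. Because the sample size and the overall-effectiveness objective both lean on this endpoint, the correction should be made before analysis.

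**What to change.** 1. Do not test the floored endpoint against 0. For the per-arm and pooled one-sample test and 95% interval on total voids, use the unfloored log ratio of follow-up to screening, with a null of no change, back-transformed to a geometric mean percent change.
2. Keep the floored measure for description and for the between-arm comparison.
3. If 25%, 20% or another non-zero criterion is kept on the floored scale, state its basis: the baseline distribution used for power, and the floored mean expected with no effect over a range of assumed SDs. The trial has one pre-treatment diary and cannot estimate that SD itself. Do not read meeting a criterion as benefit unless it exceeds that mean.
4. Describe 95.6% and 90.8% as power for the floored criterion only, not as power to show a change in voids.
5. Report the log-ratio result as change from the screening diary, not as a device effect.

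**Cost.** SAP wording only; no new data, visits or patients are needed to make the change. The result becomes relative change instead of progress toward 8, and power is lower. For a shift of ln 0.85, noncentral-t power at n=80 and n=40 is 45% and 25% at SD 0.787, or 82% and 52% at SD 0.5. At SD 0.787, 80% power would need about 186 patients: (1.960 + 0.842)² × 0.787²/0.1625² ≈ 184, plus about 2 for the t distribution. The present sample size therefore does not support the replacement test at the plan's own spread, and the SAP should say so.

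**What remains.** The diary that sets eligibility is also the reference, and there is no untreated arm, so regression to the mean persists. This was simulated with no true change, between-patient log SD 0.3, diary log SD 0.1–0.2 and true median voids of 10, 12 or 14. The log ratio shows a spurious reduction of 0.8–8.4%, significant for benefit in 7–83% of trials (n=80) and 6–54% (n=40). At median 12 the figures are 1.5–5.5%, 16–44% and 9–25%. The floored test against 0 rejects in 100% of all these cases.
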